The study includes in-clinic data collection, and data collected in a participant's home environment or when completing daily activities.

After a screening visit, the study will involve at least three clinic visits to obtain a smartphone and wireless headphones, in-clinic assessment and measures, survey data, and two home intervals for optimization of hearing assist settings.

Preceding the start of the clinical validation study, a smaller group of participants will be enrolled into a sub-study [REDACTED]. These participants will follow similar study procedures outlined in this protocol. After the completion of the sub-study, the clinical validation study will commence at a later date. This sub-study is intended to provide assurance that all of the data collection, evaluation, and data transfer tools are performing as intended prior to the start of the clinical validation study or reveal unanticipated aspects of the study. As such, these participants are a separate cohort and will not be included in any of the endpoint analyses for the pivotal study.

As described in the protocol, approximately 112 participants will be enrolled in the clinical validation study to achieve minimum 90 useable data sets. The following details outline the demographic minimum recruitment targets for the clinical validation study population:

- At least 37 enrolled participants with female sex assigned at birth
- At least 45 enrolled participants should be <60 years of age

The minimum recruitment targets for categories of hearing loss are based upon the four pure-tone average (4PTA), which is the average of hearing levels measured at 0.5, 1, 2, and 4 kHz, as measured in the ear with least hearing loss. The minimum recruitment targets for categories of hearing loss are as follows:

- Approximately 12 enrolled participants with No Impairment (4PTA: 15-25 dB HL) and perceived hearing loss where degree of hearing impairment is determined by the ear with least hearing loss.
- Approximately 37 enrolled participants with Mild hearing loss (4PTA: 26-40 dB HL) where degree of hearing impairment is determined by the ear with least hearing loss.

[figure not shown]
- Approximately 37 enrolled participants with Moderate hearing loss (4PTA: 41-60 dB HL) where degree of hearing impairment is determined by the ear with least hearing loss.

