6.1. Primary Study Endpoints

The primary endpoint for the study is:

- IOI-HA Clinic Visit 3 scores. The average total IOI-HA scores will be compared between the Self-Fit Group and Pro-Fit Group

The International Outcome Inventory for Hearing Aids (IOI-HA) is a seven-item validated questionnaire designed to be generally applicable in evaluating the effectiveness of hearing aid treatments. The inventory was developed to facilitate cooperation among researchers and program evaluators in diverse settings. The survey has seven items assessing (1) daily hearing-aid use, (2) benefit, (3) residual activity limitation, (4) satisfaction, (5) residual participant restriction, (6) impact (of hearing impairment) on others, and (7) quality of life. Each of the 7 items are scored on a 1 (poorest) – 5 (best) Likert scale and summed to obtain a total outcome score ranging from 5 to 35 where higher scores are better.

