7.3. Significance Level

The primary hypothesis test will use a one-sided significance level of 0.025. Analyses of the exploratory objectives will use 95% confidence intervals. Multiple comparison corrections will not be used.

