9.5. Primary Endpoint Analysis

The pivotal primary endpoint analysis will be performed on subjects from the Full Analysis Set (FAS) with supportive analyses also conducted on the Per Protocol (PP) and Complete Cases (CC) Analysis Sets as described below.

Missing data for the IOI-HA score at clinic visit 3 will be assumed to be missing at random (MAR). Under this assumption, the probability that the IOI-HA is missing depends only on available information (e.g., baseline demographic and other baseline characteristics). As such, the first step in modeling the missing data is to perform a logistic regression where the

outcome variable is 0 for observed cases and 1 for missing cases. This logistic regression model will include the following information available at baseline: treatment group, age, sex, race (white vs. not white), pure tone audiometry results (average across the 500, 1000, 2000, and 4000 Hz frequencies for “best” ear (i.e., lowest value of the two ears)), and otoscopy and tympanometry exam results. Factors in this model will be considered significantly related to the probability of missing if the p-value is less than 0.15. PROC LOGISTIC in SAS will be used for this analysis. The otoscopy results will be dichotomized as “normal” vs. “not normal” for the best ear. Likewise, the tympanometry exam results will be dichotomized as “type A” vs. “not type A” for the best ear. Factors which confound with one another may be removed from the model to ensure model stability and convergence.

Once the set of significant factors has been identified via logistic regression, a full information maximum likelihood (FIML) analysis will be performed using PROC CALIS in SAS to estimate the treatment effect after adjustment for significant baseline information. This approach has been shown to produce unbiased parameter estimates and standard errors under MAR [17]. This approach also provides a unique estimate of the treatment difference (PF – SF) and requires fewer decisions than multiple imputation. If there are no baseline factors identified through the logistic regression analysis which are significantly related to missingness and if there is no missing data for any of the baseline factors, the parameter estimate of the treatment effect will be the arithmetic mean difference (PF – SF) between the two groups but with a smaller standard error than using only complete cases.

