The process works by estimating a likelihood function for each study subject based on the baseline factors that are present so that all the available data are used. Model fit information is derived from a summation across fit functions for individual subjects, and, thus, model fit information is based on all subjects. With missing data, the FIML fit function [18] is computed for each set of subjects with the same unique pattern of missing values—a casewise likelihood. So, an i subscript is used in the equation below to show that the fit function is for each particular subject:

$$\log L_i = -\frac{k_i}{2} \log(2\pi) - \frac{1}{2} \log|\Sigma_i| - \frac{1}{2} (\mathbf{Y}_i - \boldsymbol{\mu}_i)^T \boldsymbol{\Sigma}_i^{-1} (\mathbf{Y}_i - \boldsymbol{\mu}_i)$$

where \log is the natural logarithm (with base e), π is the mathematical constant, Σ_i is the population covariance matrix, \mathbf{Y} is vector of observed variables, $\boldsymbol{\mu}_i$ is the vector of their means, and the superscript T is the matrix transpose function. The subscripts i denote individual subjects in which the \mathbf{Y}_i vectors differ in length depending on the number of non-missing data values. Similarly, matrices Σ_i and $\boldsymbol{\mu}_i$ vary by deleting rows and columns for missing variables. The sum of the individual log likelihoods is then computed. This process approach allows one to use all the available information in the variables. Additionally, as can be seen from this likelihood function, this approach assumes the IOI-HA scores follow a normal distribution.

Because the study hypothesis is a test of non-inferiority, a Wald-type 95% two-sided confidence interval for the treatment effect will be computed (i.e., treatment effect parameter

estimate +/- 1.96*(Standard error of the estimated treatment effect)) and compared to the non-inferiority margin of 3. If the upper 95% confidence bound for the treatment effect (defined such that higher values favor the pro-fit group) is less than or equal to 3, the null hypothesis will be rejected and the self-fit treatment arm will be considered non-inferior to that of the pro-fit treatment arm.

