The pivotal primary endpoint analysis using the above methodology will be based on the Full Analysis Set where all randomized subjects are included in the analysis and subjects will be analyzed according to the treatment group to which they were randomized. A supportive analysis will also be performed using the Per Protocol Analysis Set where subjects will be analyzed according to the treatment received.

A Complete Cases analysis using only those subjects who have a non-missing outcome for the IOI-HA survey will also be performed using a two-sample independent non-inferiority t-test assuming equal variances. The two-sided 95% confidence interval will be reported for the (Pro-Fit – Self-Fit) mean difference. In the event there are substantial departures from the equal variances assumption, a two-sample t-test assuming unequal variances will be performed similarly.

If the non-inferiority hypothesis is rejected using the Full Analysis Set, a gatekeep strategy will be used to test for superiority to determine if the treatment effect (i.e., mean difference) is statistically different than 0 using the same two-sided significance level of 0.05. If the upper two-sided 95% confidence bound for the treatment effect (Pro-Fit – Self-Fit) is less than or equal to 0, superiority of the Self-Fit arm will also be concluded in addition to non-inferiority.

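### The pivotal IOI-HA model admits 4PTA, age and sex only if they predict missing scores, never for their relation to the score; fixing them in advance is an inexpensive option, not the repair of an error

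*SAP*

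**What the plan says.** SAP section 6.1 defines the primary endpoint: "IOI-HA Clinic Visit 3 scores. The average total IOI-HA scores will be compared between the Self-Fit Group and Pro-Fit Group". The score is taken once, so it has no baseline value to adjust for.

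SAP section 9.5 sets the pivotal analysis in two steps. A logistic regression with missing or observed IOI-HA as the outcome is fitted on treatment, age, sex, race, better-ear 4PTA, otoscopy and tympanometry. The selection rule is: "Factors in this model will be considered significantly related to the probability of missing if the p-value is less than 0.15". FIML then estimates the treatment difference, adjusted for the selected factors only. If no factor is "significantly related to missingness and if there is no missing data for any of the baseline factors", the estimate is the plain difference in means, which the SAP says will have a smaller standard error than a complete-case analysis. A further sentence gives some discretion: "Factors which confound with one another may be removed from the model to ensure model stability and convergence".

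The upper limit of "estimate +/- 1.96*(Standard error of the estimated treatment effect") is compared with the margin of 3. SAP section 7.3 says: "The primary hypothesis test will use a one-sided significance level of 0.025". After non-inferiority, "a gatekeep strategy will be used to test for superiority", again using the 95% limit. Randomisation is unstratified (SAP section 7.2), and the complete-cases analysis is an unadjusted t-test.

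**The concern.** A covariate narrows the confidence bound to the extent that it predicts the outcome. The SAP selects covariates on a different property, whether they predict dropout. A 4PTA that strongly predicted IOI-HA but not dropout would usually be left out. One that predicted dropout by chance would enter, useful or not. The covariate set of the pivotal estimate is therefore settled by who drops out.

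At stake is the width of the upper bound that decides non-inferiority and then superiority. If 4PTA, age or sex predict IOI-HA, that bound is wider than the collected data require. If they do not, there is nothing to gain.

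**Working it through.** **Inputs from the documents.** 112 randomised 1:1 in blocks of 4 (SAP sections 7.1 and 7.2); margin 3; one-sided level 0.025; "approximately 112 participants will be enrolled in the clinical validation study to achieve minimum 90 useable data sets" (SAP section 4). The implied loss is 1 − 90/112 = 19.6%, used as a working missing rate of 20%. It is not a cap on missing IOI-HA.

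**Assumptions.** SD and power are redacted, so the sample size cannot be reproduced. For 45 per arm and true difference 0, the normal formula SD = 3·√(45/2)/(1.960 + z) gives 5.08 for 80% power (z = 0.842) and 4.39 for 90% (z = 1.282). I use SD 4.4 for precision and 5.02 for power (80% for an unadjusted t-test). The R² of 4PTA, age and sex with IOI-HA is not given, so it is varied over 0, 0.05, 0.10 and 0.20. Baseline data are taken as complete and the FIML standard error as using divisor n.

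**1. How often the screen admits a factor** (20,000 simulated trials per scenario, no factor related to dropout).

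| Missing | 20% | 10% | 5% |
|---|---|---|---|
| 4PTA selected | 16.1% | 16.7% | 14.9% |
| No baseline factor selected | 37.5% | 44.1% | 54.6% |
| At least one selected | 62% | 56% | 45% |

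When 4PTA does predict dropout moderately (odds ratio 1.5 per SD, 20% missing, 3,000 trials), it is still missed in about 40% of trials.

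**2. Gain and cost by formula.** The standard error is multiplied by √(1 − R²), giving 1.000, 0.975, 0.949 and 0.894: a fall of 0%, 2.5%, 5% and 11%. With 90 scores, k useless covariates multiply it by √(87/(87 − k)) = 1.006, 1.012 and 1.018 for k = 1, 2, 3. Break-even for three covariates on the standard error is R² = 3/87 = 0.034.

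**3. Calibration of the 1.96 bound.** The actual one-sided error is P(t_df > 1.96·√(df/90)). With no covariate (df 88) it is 2.79%; with three (df 85) it is 3.01%. The corrected bound t_0.975,df·√(90/df) is 1.025 (df 88) or 1.044 (df 85) times 1.96. Simulated error at a true difference of 3 (40,000 trials; R² = 0, 0.10, 0.20; Monte Carlo SE 0.08 points):
- SAP rule with 1.96: 2.93%, 2.76%, 2.89%
- three fixed plus screen, with 1.96: 3.09%, 3.00%, 3.03%
- three fixed plus screen, with the t bound: 2.52%, 2.41%, 2.46%

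**4. Simulated effect on precision and power** (20% missing; 20,000 trials per scenario; percentages and paired differences use unrounded values). The full fix is three fixed covariates plus the screen, with the t bound.

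| Assumed R² | 0 | 0.05 | 0.10 | 0.20 |
|---|---|---|---|---|
| SD of estimate, SAP rule | 0.934 | 0.923 | 0.930 | 0.915 |
| SD of estimate, three fixed plus screen | 0.950 | 0.918 | 0.905 | 0.848 |
| Paired difference (Monte Carlo SE) | −0.015 (0.001) | +0.005 (0.002) | +0.025 (0.002) | +0.067 (0.003) |
| Half-width, SAP as written | 1.801 | 1.796 | 1.786 | 1.771 |
| Half-width, SAP rule with t bound | 1.857 | 1.852 | 1.842 | 1.826 |
| Half-width, full fix | 1.885 | 1.840 | 1.789 | 1.687 |
| Full fix against SAP rule with t bound | +1.5% | −0.7% | −2.9% | −7.7% |
| Full fix against SAP as written | +4.7% | +2.4% | +0.1% | −4.8% |
| Power, SAP as written (SD 5.02) | 80.5% | 81.2% | 81.0% | 82.5% |
| Power, SAP rule with t bound | 78.8% | 79.6% | 79.3% | 81.0% |
| Power, full fix | 77.5% | 80.0% | 81.3% | 86.7% |

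A hand check agrees: 4.4·√(2/45) = 0.928 with no covariate, and 0.928 × 1.018 = 0.944 with three useless ones. Spreading R² equally over the three covariates gives similar SDs.

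Break-even R² is 0.035 when both sides use the t bound. For the t bound with three covariates against the 1.96 bound with none, it is 0.083.

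**5. Why the screen should stay.** Suppose tympanometry drives dropout in one arm (50% against 12%; 20% in the other arm; 25% not type A) and correlates 0.4 with the outcome. The bias is 0.10 under the SAP rule, 0.10 with three fixed covariates plus the screen, and 0.36 with the screen deleted.

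**The case against.** The strongest reply is that nothing is broken. The logistic step is a missing-data device, stated in advance. An unadjusted comparison in a randomised trial is legitimate, the sample size rests on an unadjusted t-test, and the screen itself causes no type I error problem. Prognostic adjustment is then a preference whose benefit rests on an R² that the documents do not contain. Recruitment targets on hearing level, age and sex control the sample mix; they are not evidence that these factors predict IOI-HA. All of this stands, and it is why the point is only a suggestion.

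Second, the package is not free. Against the bound as written it widens the interval at R² of 0 and 0.05 and breaks even near 0.10; power at R² = 0 falls from 80.5% to 77.5%. That also stands. Part of the cost comes from the t correction, a calibration matter separate from covariate choice, which applies even if no covariate is added. It belongs with the change because adding covariates takes the error under 1.96 from 2.79% to 3.01%. It does depend on the software reporting a divisor-n standard error, which the documents do not confirm.

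Third, the share of trials in which some factor enters depends on assumed prevalences for race, otoscopy and tympanometry. Other choices gave about 54% to 63% at 20% missing. At 5% missing there are only about 6 events (112 × 0.05 = 5.6) for seven candidates. In one check the logistic model showed separation or near-separation in about 55% of trials, so that column is soft. The 84% omission rate for 4PTA is firmer: it follows almost directly from a 0.15 threshold with no association.

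**Conclusion.** The point holds as an optional improvement. SAP section 9.5 admits baseline factors to the pivotal model only for their relation to missingness, and nothing elsewhere in the plan admits one for its relation to IOI-HA. No bias follows from leaving out a factor unrelated to dropout, and no stated power is missed.

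The loss is precision, of unknown size. Comparing like with like (both with the t bound), fixing three covariates pays above R² of about 0.035. Against the SAP bound as written, it pays above about 0.08 to 0.10. At R² = 0.20 the full fix raises simulated power from 82.5% to 86.7%; at R² = 0 it lowers it from 80.5% to 77.5%. Separately, if the standard error uses divisor n, the 1.96 bound slightly exceeds the 0.025 level.

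These sizes rest on assumed R², SD, missing rate and complete baseline data. Choosing 4PTA, age and sex is a judgement: the plan sets recruitment targets on them and already lists them as candidates.

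**What to change.** Amend SAP section 9.5 before any dropout or outcome data are seen:

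1. Leave the logistic missingness model as it is. State that the permission to remove confounded factors applies to that model, for convergence, and cannot remove the fixed covariates from FIML.
2. In the FAS and per-protocol FIML models, always include treatment, better-ear 4PTA (continuous), age and sex. Keep the p < 0.15 screen to add race, otoscopy and tympanometry.
3. Reword the fallback: if no further factor is identified and no baseline data are missing, the estimate is the PF − SF mean difference adjusted for 4PTA, age and sex. Drop the claim of a smaller standard error.
4. Multiply the ML standard error by √(n/(n − 2 − k)) and replace 1.96 by the 97.5th percentile of t with n − 2 − k degrees of freedom, where n is the number of observed scores and k the number of covariates besides treatment. Use the same bound for superiority. First confirm that the reported standard error uses divisor n.
5. Keep the unadjusted complete-cases t-test as supportive.

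The cost is SAP wording only; every covariate is already collected. If all three fixed covariates prove useless, the standard error rises by about 1.8%. The t correction widens the bound by 2.5% (no covariate) to 4.4% (three), which is the price of restoring 2.5% error. The correction is exact only with complete baseline data and approximate otherwise. A sponsor holding earlier IOI-HA data could estimate R² before deciding.

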9.6. Significance Level

The primary hypothesis tests will use a one-sided significance level of 0.025. Analyses of the exploratory objectives will use 95% confidence intervals. Multiple comparison corrections will not be used.

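### The pivotal FIML interval uses a maximum-likelihood standard error with 1.96, so the one-sided error is about 0.027 to 0.030 rather than 0.025

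*SAP*

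**What the plan says.** Both documents set the level of the primary test. SAP 7.3 states "The primary hypothesis test will use a one-sided significance level of 0.025", and Protocol 9.6 says the same. Protocol 9.2 expresses the rule as a one-sided 97.5% upper bound for Pro-Fit minus Self-Fit of no more than 3.

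SAP 9.5 describes the pivotal analysis:

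- Baseline factors with p < 0.15 in a logistic model for missingness are carried into a FIML analysis in PROC CALIS, to adjust the treatment effect.
- The likelihood for each participant is "based on the baseline factors that are present so that all the available data are used".
- When no factor is selected, and "if there is no missing data for any of the baseline factors", the estimate is the arithmetic mean difference "between the two groups but with a smaller standard error than using only complete cases".
- The confidence limits are "estimate +/- 1.96*(Standard error of the estimated treatment effect"), and the upper limit is compared with 3.
- If non-inferiority is shown, the upper limit is compared with 0 for superiority, "using the same two-sided significance level of 0.05".
- The supportive complete-cases analysis is a "two-sample independent non-inferiority t-test assuming equal variances".

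No CALIS model statement, degrees-of-freedom correction or t quantile is given for the pivotal analysis.

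**The concern.** IOI-HA has no baseline or interim measurement (Protocol 8.1.4.7), so no earlier score can stand in for a missing one. In the case that the quoted clause describes, the pivotal and complete-cases analyses use the same people and give the same estimate. A shorter interval for one of them cannot then reflect extra information.

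Two things follow. First, the interval that decides non-inferiority, and then superiority, is slightly too short, and the error always favours a claim. Second, the wording can be read as saying that FIML recovers information from participants without a score. In this case it does not, and agreement between the pivotal and complete-cases results would say nothing about sensitivity to missing data.

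**Working it through.** **Inputs.** One-sided level 0.025 (SAP 7.3). Critical value 1.96 and margin 3 (SAP 9.5). 112 randomized 1:1, 56 per group (SAP 7.1, 7.2). At least 90 usable data sets (SAP 4). Six factors besides treatment can be selected: age, sex, race, best-ear pure-tone average, otoscopy, tympanometry (SAP 9.5). The SD is redacted, but the error rate does not depend on it.

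**The plan's own figure.** 1 − Φ(1.96) = 0.0250. This reproduces the stated level, but only in the large-sample limit.

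**Step 1: what FIML estimates.** With complete covariates x, the likelihood in SAP 9.5 factorises as f(score | treatment, x) × f(treatment, x). A participant without a score enters only the second factor, which carries nothing about the treatment effect. Direct maximisation on simulated data with N = 112 confirmed this:

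| Covariates | Scores observed | FIML estimate | Completer OLS | FIML SE | OLS SE (n − p) | OLS SE (divisor n) |
|---|---|---|---|---|---|---|
| 0 | 95 | 0.64517 | 0.64517 | 0.17628 | 0.17817 | 0.17628 |
| 1 | 92 | 0.58936 | 0.58936 | 0.18701 | 0.19014 | 0.18701 |
| 2 | 93 | 0.23339 | 0.23339 | 0.21520 | 0.21998 | 0.21520 |

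The whole gap is the factor √((n − p)/n), with p = 2 + number of selected factors. With no factor it is √(88/90) = 0.989 at n = 90 and √(110/112) = 0.991 at n = 112.

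The identity is conditional. In a further example, one factor was made missing for 5 participants who had a score. FIML then gave 1.069, against 1.097 for OLS on the 85 left.

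**Step 2: exact one-sided error** for normal scores with equal variances:

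error = P(T with n − p df > 1.96 × √((n − p)/n))

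| Scores observed | 0 factors | 1 | 2 | 3 | 6 |
|---|---|---|---|---|---|
| 90 | 0.0279 | 0.0286 | 0.0293 | 0.0301 | 0.0325 |
| 100 | 0.0276 | 0.0282 | 0.0289 | 0.0296 | 0.0316 |
| 112 | 0.0273 | – | – | – | – |

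With all 112 observed there is no missingness to model, so no factor can be selected. At n = 90 with no factor, 1.96 alone gives 0.0266 and the divisor alone 0.0263. The two-sided error is 2 × 0.0279 = 0.0558.

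**Step 3: how many factors are likely.** Suppose no factor predicts missingness and the six tests are independent at 0.15. Zero or one is then selected with probability 0.78, and three or fewer with probability 0.994. The average error at n = 90 is 0.0286.

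**Step 4: simulation including the selection step** (true difference 3, 112 randomized, about 20% missing, 60,000 runs per scenario, Monte Carlo SE 0.0007). With no true predictor of missingness, rejection was 0.0282 under the SAP rule and 0.0247 with n − p and t. With two true predictors it was 0.0296 and 0.0249.

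**Step 5: effect on the bound.** The correct multiplier on the FIML standard error is t(0.975, n − p) × √(n/(n − p)). At n = 90:

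- No factor: 1.9873 × √(90/88) = 2.010, and 2.010/1.96 = 1.025, so 2.5% wider.
- Three factors: 1.9883 × √(90/85) = 2.046, and 2.046/1.96 = 1.044, so 4.4% wider.

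For an assumed SD of 4 and 45 per group, the n − p standard error is 4 × √(2/45) = 0.843. With no factor the half-widths are 1.9873 × 0.843 = 1.676 and 1.96 × 0.989 × 0.843 = 1.634, a shift of 0.04 points. With SD 6 the shift is 0.06. With three factors (taking 4 to 6 as the residual SD) it is 0.07 to 0.11.

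**The case against.** The strongest objection is size. In the case the clause describes, the error is 0.0273 to 0.0279. In simulation at n = 90 with no factor, SD 4 or 6 and a true difference of 0 or 1, the SAP rule and the t rule disagreed in only 0.6% to 1.8% of trials. Ninety is also a floor: a usable data set needs complete endpoint data, while the primary analysis needs only an IOI-HA score, so n may be higher. At n = 105 with no factor the error is 0.0275 and the shift 0.03 to 0.05 points. This stands, and it limits the weight of the point.

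A Wald interval with 1.96 is openly prespecified and common, and the complete-cases t interval will be reported beside it. That makes a discrepancy visible, but the shorter interval remains the one that decides.

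The documents do not say which divisor the software reports. If it is n − 1, the error for 0 to 3 factors is 0.0268 to 0.0294, so the conclusion is unchanged. IOI-HA is also a bounded sum of seven items, so the fourth decimal should not be taken literally.

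The model itself is not settled. If factors entered as auxiliary variables, or were partly missing, FIML could gain real precision. The SAP's reference to adjustment favours covariates, and its statement that the estimate is the arithmetic mean difference rules out such a gain in the quoted case. Finally, the correction proposed below is exact only with complete covariates.

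**Conclusion.** The concern holds. With complete baseline factors entered as covariates, the pivotal FIML estimate is the completer regression. Its smaller standard error is a divisor effect, not recovered information. Together with 1.96, this puts the one-sided error at about 0.027 to 0.030 for 90 to 112 observed scores and up to three selected factors. The value of 0.0325 with all six selected at n = 90 is a very unlikely ceiling.

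This rests on normal scores, equal variances, complete covariates and division by n. The practical effect is small: 0.04 to 0.11 points at n = 90 under an assumed SD of 4 to 6, which matters only for a bound very close to 3, or to 0 at the superiority step. It should still be corrected, because it affects the single pivotal test, always in favour of a claim, and costs almost nothing to put right.

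**What to change.** In SAP 9.5:

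1. Compute the pivotal interval with the FIML standard error multiplied by √(n/(n − p)) and the t quantile on n − p degrees of freedom. Here n is the number with an IOI-HA score and p is 2 plus the number of selected factors. When all selected factors are complete, ANCOVA in GLM or MIXED gives the same result. Use the same bound for the superiority step.
2. If a selected factor is missing for someone with an IOI-HA score, keep FIML so that this person is not dropped. Apply the same correction and state that it is then approximate.
3. Write out the CALIS model statement, with the selected factors as covariates.
4. Delete the clause on the smaller standard error. State instead that, with complete baseline factors, participants without an IOI-HA score do not inform the treatment estimate.

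The cost is a few lines of text and one rescaling step, with no extra data. The interval widens by about 2 to 4% in realistic cases (6% with all six factors at n = 90), a very small loss of power. With no factor selected and complete baseline factors, it becomes identical to the equal-variance complete-cases t interval on the same participants.
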